2.0 STUDY OBJECTIVES

Hypothesis / Study Objective/ Purpose:

In our recent study using the TrueTear™ intranasal neurostimulator (ITN) in patients with dry eye disease (Dieckmann et al. ARVO 2017, unpublished observation) and concurrent neuropathic symptoms, some patients that suffered from neuropathic pain or photoallodynia, reported immediate relief of pain or photoallodynia after a single 3-minute use of ITN.

Thus, we hypothesize that the stimulation through the ethmoidal nerve in the nasal cavity may have an inhibitory effect on the primary TG interneurons and block the ocular pain signaling to the brain.

We propose a non-randomized, cross sectional, open-label, single arm pilot trial for treatment of neuropathic corneal pain (NCP) with ITN with the following specific aims:

Specific Aims:

1. To elucidate the efficacy of ITN in ameliorating pain among neuropathic corneal pain patients.
2. To elucidate the safety, efficacy, longevity of ITN in ameliorating pain among neuropathic corneal pain patients during a 90-day period with daily use.
3. To assess quality of life changes by treating neuropathic corneal pain with ITN during a 90-day period with daily use.

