4.0 SUBJECT SELECTION

4.1. Subject Inclusion Criteria:

1. Age ≥ 22 .
2. Ability to consent to study.
3. Symptoms of neuropathic corneal pain for at least 3 months, such as burning, stinging, light sensitivity, discomfort or pain.
4. Positive *in vivo* confocal microscopy (IVCM) findings for NCP such as presence of microneuromas and decreased nerve density. The presence of positive IVCM findings serves in lieu of skin biopsies as proof of nerve injury.
5. Fifty percent or more relief of pain or discomfort after instillation of Proparacaine eye drops as measured by the Visual Analogue Scale (VAS).

4.2. Subject Exclusion Criteria:

1. Clinically significant acute ocular surface diseases, such as active infectious keratitis or recent ocular surgery in the past 3 months.
2. Chronic or recurrent epistaxis, coagulation disorders.
3. Nasal or sinus surgery or significant trauma to the nose.
4. Severe nasal airway obstruction or vascularized nasal polyps.
5. Cardiac demand pacemaker, implanted or wearable defibrillator, or other implanted electronic device in the head or neck.
6. Chronic or recurrent nosebleeds
7. Bleeding disorder or another condition that can lead to increased bleeding
8. Known hypersensitivity (allergy) to the hydrogel material that contacts the nasal mucosa
9. Disabling arthritis, neuropathy, or limited motor coordination affecting self-handling of the device.
10. Allergic to benzalkonium chloride (the Co-Investigators who administer the eye drops ask all patients if they are allergic to any eye drop preservatives before proceeding with the eye drops)

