5. STUDY DEVICE

5.1 Study Device Information

The ITN delivers small electrical currents to the inner cavity of the nose, gently activating nerves that stimulate the body's natural tear production system.

The device consists of four distinct parts (Figure 1):

1. A reusable Base Unit, which produces the electrical stimulation waveform.
2. A disposable Tip Assembly that inserts into the nasal cavity and stimulates the target intranasal tissue.
3. A reusable Cover to protect the Tip Assembly.
4. A Charger, which recharges the battery inside the Base Unit.

Figure 1: The TrueTear® Intranasal Neurostimulator (ITN) components.

1. Base Unit

When activated, the base unit provides electrical pulses to the Tip Assembly. The strength of these pulses is controlled by two buttons, with five different levels available, indicated by the number of illuminated LEDs on the base unit. The Base Unit can only be activated when a Tip Assembly is present. The base unit also records the use of the device, stimulation level and

Tufts Medical Center

duration, in internal memory. Upon return of the device, this information will be downloaded from the device and summarized as described in the Statistics section below.

2. Tip Assembly

The Tip Assembly is specially designed to allow the participant to easily apply stimulation to the target areas within the nose. The Tip Assembly connects to the Base Unit and contains a hydrogel (similar to the material used in contact lenses) that touches the inside of the nose to provide stimulation. The disposable Tip Assemblies are removed and replaced at least daily; a separate Cover can be used to protect the Tip Assembly when not in use.

3. Cover

The cover may be slipped over the top of the Base Unit and Tip Assembly between uses.

4. Charger

The Base Unit may be recharged by removing the Tip Assembly and placing it onto the Charger. Charging takes under 4 hours, and a green LED indicates that the process has completed.

5. Device Accountability

The investigator will be responsible for maintaining a device accountability log(s) that will track device usage for all study participants. Information tracked will include date of device receipt, lot and/or serial number, date of device usage or return (if applicable), subject ID, the occurrence of any device malfunctions or failures.

6. Labeling, Packaging, Storage, and Return or Disposal of Study Devices

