5.2 Study Device Compliance/Adherence

Directed questioning using the (Ocular Tolerability and Compliance Questionnaire – Appendix VI) will be administered by the investigator or research staff. Results on the participants' compliance and adherence to the study protocol and study device will be recorded on the paper case report form (CRF). During the study, all concomitant medication treatment regimens, ocular hygiene treatments (i.e., lid scrubs and warm compresses), or insertion of punctal plugs will be kept constant as permitted by accepted medical practice. If one of the aforementioned treatment regimens needs to be modified, the participant may be withdrawn based on the investigator's discretion.

Participants must be compliant with IVCM imaging on the study visit or they will be withdrawn. Subjects who are withdrawn may be replaced by new enrolled subjects to maintain the sample size.

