7.4 Follow-up Procedures

Subjects will come back for a 1st visit after the screening visit; 2nd visit at 45 days (\pm 1 week) following the first visit, and 3rd visit following 90 days after the first visit (\pm 2 weeks). All of the procedures done at the baseline visit will be done in the 2nd and 3rd visits (see flowchart).

In addition, subjects will be asked about their usage of the ITN. Ocular safety and tolerability questionnaire (appendix VI) will be administered in the 2nd and 3rd visit. The subject will be asked to complete a diary every day to record any pain symptoms (Appendix VII). The subject will be asked to send their pain diary weekly to the study coordinator, in however method works for the subject to ensure compliance with the ITN. They will also need to bring the diary to each study visit, to ensure compliance.

Ocular Tolerability Questionnaire (Appendix VI): This questionnaire assesses tolerability of the ITN device. It assesses symptoms of discomfort in each eye after ITN use.

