Appendix VI: Ocular Tolerability and Compliance Questionnaire

After you used the TrueTear® neurostimulation, how intensely have you experienced the following symptoms?

Itching

Right Eye:	None	Trace	Mild	Moderate	Severe
Left Eye:	None	Trace	Mild	Moderate	Severe

Burning Sensation

Right Eye:	None	Trace	Mild	Moderate	Severe
Left Eye:	None	Trace	Mild	Moderate	Severe

Foreign Body Sensation

Right Eye:	None	Trace	Mild	Moderate	Severe
Left Eye:	None	Trace	Mild	Moderate	Severe

Have you experienced any other symptoms after undergoing the study tests?

YES NO

If yes, which one(s) _____

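### The only tolerability form shown grades eye symptoms and nothing in the nose, where the device is applied; the causality wording also needs reconciling

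*Combined protocol and SAP*

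**What the plan says.** Aim 2 in section 2.0 is "To elucidate the safety, efficacy, longevity of ITN in ameliorating pain among neuropathic corneal pain patients during a 90-day period with daily use", and 10.2 lists safety and tolerability among the secondary outcomes. According to 5.1, the disposable tip carries a hydrogel that "touches the inside of the nose to provide stimulation". According to 5.3, the tips go into both nostrils together, at least twice a day. Section 4.2 recognises nasal risk: it excludes people with recurrent nosebleeds, nasal surgery or trauma, severe obstruction or vascularised polyps, and "Known hypersensitivity (allergy) to the hydrogel material that contacts the nasal mucosa".

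On measurement, 7.4 Follow-up Procedures schedules Appendix VI at visits 2 and 3 and says: "This questionnaire assesses tolerability of the ITN device. It assesses symptoms of discomfort in each eye after ITN use". Section 5.2 adds: "Directed questioning using the (Ocular Tolerability and Compliance Questionnaire – Appendix VI) will be administered by the investigator or research staff". Appendix VI grades itching, burning and foreign body sensation from none to severe, for the right and the left eye. It ends with a yes/no item with free text: "Have you experienced any other symptoms after undergoing the study tests".

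On adverse events, 8.1 and 10.6 rate severity as serious or not serious, and causality in three degrees of relatedness to a study medication. Section 9.1 defines an adverse event by reference to a pharmaceutical product. Elsewhere it speaks of the study device and allows a finding that an event is not related to it. It lists two seriousness criteria, fatal and life-threatening, whereas 10.6 defers to an institutional definition.

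**The concern.** The form that is meant to show how well the device is tolerated looks only at the eyes, while the device acts on the nasal lining. Over 90 days at the minimum frequency, a participant applies it about 90 × 2 = 180 times. Nasal pain, irritation or bleeding are the complaints one would expect to ask about first, and the form does not ask about them.

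At stake is one secondary outcome and part of Aim 2. The tolerability table could look favourable because it describes the eyes, while the nasal experience appears only as whatever participants happened to mention, with no grade. A reader could not tell a well-tolerated device from one whose nasal effects were under-reported or never rated.

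The causality wording matters for the same report. If staff follow 8.1 for one event and 9.1 for a similar one, the two may be classified differently.

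**Working it through.** The plan gives no figure to reproduce here. The check is a count of what is graded, followed by a comparison of passages.

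**1. Graded content of Appendix VI.** 3 symptoms × 2 eyes = 6 graded entries, of which 0 are nasal. Over the two scheduled administrations (visits 2 and 3), 6 × 2 = 12 graded entries per participant, again 0 nasal.

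**2. Other routes by which a nasal symptom could be recorded.**

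| Route | Names the nose? | Gives an intensity grade for a nasal symptom? |
|---|---|---|
| Appendix VI open item | No; worded for the study tests, not device use | No; yes/no and free text |
| Adverse event questions (8.1, 9.1) | No; of the two examples in 8.1, one is general and one asks about the eyes | No; severity is serious or not serious |
| Examination in 8.1 | No; it is an eye examination | No |
| Procedure lists (7.1, 7.3, 7.4) | No nasal check listed | No |
| OPAS non-eye pain (Appendix III) | No; it names temples, back of head and cheek | Rates pain, but not nasal pain separately and not after device use |
| Diary (Appendix VII) | No; discomfort and pain before and after use, with no nasal site in the text shown | A nasal rating could not be separated from an ocular one |
| Device log (5.1) | No | No; it shows behaviour, not symptoms |

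Several routes could therefore bring in a nasal event. None yields a graded nasal symptom linked to device use.

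**3. Why the adverse event route does not fill the gap.** An unpleasant but non-serious nasal symptom and a trivial one both fall under not serious. Appendix VI separates trace, mild, moderate and severe for the eyes; the adverse event record makes no such distinction for the nose.

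**4. Causality and seriousness, side by side.**
- 8.1 and 10.6: possible, probable or definite relation, to a medication. No category for unrelated events.
- 9.1: an unrelated finding is allowed and must be documented, and a questionable relation is counted as associated. Both refer to the device, although the adverse event definition refers to a pharmaceutical product.
- Seriousness: 9.1 prints two criteria; 10.6 points to an institutional definition that the document does not reproduce.

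**The case against.** The strongest reply is that the plan may already contain what is missing. Sections 7.2 and 7.4 Study Specific Procedures speak of safety and tolerability questionnaires in the plural, and 10.6 promises directed questioning without naming a form. The flowchart is not in the text reviewed, and Appendix VI shows no compliance item despite its title. A reader might infer that graded nasal tolerability will certainly not be obtained. The documents do not support that; they support only that no instrument shown obtains it.

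A second reply is that nasal events are not ignored. Participants are asked about adverse events at study visits, all observed or volunteered events are recorded, unscheduled visits include an adverse event review, and the device log would show falling use: "The base unit also records the use of the device, stimulation level and" duration. This stands. To infer that nasal safety is not captured at all would be wrong. What is missing is the grade and a prompt that names the nose.

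A reader might also infer that 9.1 and 10.6 conflict on seriousness. That is unproven, because the institutional definition is not shown and may agree with 9.1. On causality, 8.1 and 10.6 may be meant only for events already judged related, but they do not say so.

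Two further inferences do not hold. Missing forms from people who leave before visit 2 are ordinary attrition: the plan gives no timing of dropout, and adverse events are followed after withdrawal. The lack of an Appendix VI form before first use is a matter of preference, since the diary already rates discomfort and pain before and after use.

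Finally, this is an open-label pilot of a device the protocol describes as FDA-approved, and the primary endpoint (VAS pain) is untouched. That limits the weight of the point but does not answer it, since the plan itself made tolerability an outcome.

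**Conclusion.** The point holds in a limited form. None of the 6 graded entries on the one tolerability form shown is nasal, and the routes that could record a nasal symptom give it no intensity grade of its own. A low nasal count from this trial could not be read as good nasal tolerability. How many nasal symptoms would go unmentioned cannot be estimated from the documents, so the count of graded items is the only size offered.

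The conclusion assumes that Appendix VI is shown in full and that the flowchart holds no separate nasal form. If either assumption is wrong, a citation would settle the main point. The causality wording is a smaller matter: as printed, the sections do not offer the same categories or refer to the same product. For seriousness, the plan needs only to say which definition applies. This is an inexpensive improvement that should be made, and it does not threaten the primary analysis.

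**What to change.** 1. Add graded nasal items to Appendix VI, for example pain, bleeding and irritation, on its existing none-to-severe scale. Three such lines would take the form from 6 to 9 graded entries per visit.
2. Reword the open item so that it refers to use of the device.
3. If a nasal form already exists in the flowchart, cite it in 7.4 Follow-up Procedures and in 10.6 instead.
4. Use one causality scale in 8.1, 9.1 and 10.6 that refers to the device and includes a not-related category, and refer the adverse event definition in 9.1 to the device.
5. State whether the seriousness criteria of 9.1 or the institutional definition named in 10.6 apply.

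The cost is a few questionnaire lines and some edited sentences, with no new visit. The downside is slightly more form-filling and, because people will now be asked, a somewhat higher reported count of nasal events. The report should say that this count was prompted.

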7.5 Unscheduled Visits

Tufts Medical Center

If the subject reports to the Cornea Department for a visit that is not related to the study, only a review of adverse assessments will be required per the study.

7.6 Early Termination

If a subject withdraws or is withdrawn from the study prior to completion of all study visits, there will be no additional procedures performed

8. SAFETY AND EFFECTIVENESS ASSESSMENTS

8.1 Safety Assessments

The primary safety variable monitored will be the occurrence of adverse events. The severity of each adverse event observed will be evaluated as serious or not serious and the occurrence will be evaluated as expected or unexpected. The relationship of the event to the study medication will be assessed by the investigator as possibly, probably, or definitely related. Safety variables will be evaluated at all study visits. If adverse events occur, the first concern will be the safety of the study participants. Any serious adverse event occurring during the study period will be immediately reported to TUFTS IRB. At each visit throughout the study, the investigator will begin querying for adverse events by asking each subject a general, non-directed question such as "How have you been feeling since the last visit?" or "How have your eyes been since the last visit?"

A comprehensive eye examination including best-corrected visual acuity, evaluation of the condition of conjunctiva, cornea, anterior chamber, iris/pupil, lens, will be performed.

Withdrawal from the study will happen if any of the following occurs:

- Investigator determination that it is not in the best interest of the subject to continue participation.
- Subject's wish to withdraw for any reason.

After being withdrawn, subjects will be followed according to each case until the adverse event is resolved.

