9. ADVERSE EVENT RECORDING AND REPORTING

9.1 Recording Requirements

Adverse Events (AEs)

An adverse event is any untoward medical occurrence in a clinical investigation subject administered a pharmaceutical product, regardless of causal attribution.

Serious Adverse Events (SAEs)

A serious adverse event is any adverse event that meets any of the following criteria:

- Is fatal (i.e., the adverse event actually causes or leads to death)
- Is life threatening (i.e., the adverse event, in the view of the investigator, places the patient at immediate risk of death)

Unanticipated Problems

According to the Office of Human Research Protections (OHRP), unanticipated problems includes “any incident, experience, or outcome that meets all of the following criteria:

1. unexpected (in terms of nature, severity, or frequency) given (a) the research procedures that are described in the protocol-related documents, such as the IRB-approved research protocol and informed consent document; and (b) the characteristics of the subject population being studied;
2. related or possibly related to participation in the research (in this guidance document, possibly related means there is a reasonable possibility that the incident, experience, or outcome may have been caused by the procedures involved in the research); and
3. suggests that the research places subjects or others at a greater risk of harm (including physical, psychological, economic, or social harm) than was previously known or recognized.

Unanticipated Adverse Device Effect (UADE)

Unanticipated adverse device effect means any serious adverse effect on health or safety or any life-threatening problem or death caused by, or associated with, a device, if that effect, problem, or death was not previously identified in nature, severity, or degree of incidence in the investigational plan or application (including a supplementary plan or application), or any other unanticipated serious problem associated with a device that relates to the rights, safety, or welfare of subjects.

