Research subjects will be routinely questioned about adverse events at study visits. All observed or volunteered adverse events (serious or non-serious) and abnormal test findings, regardless of study group or suspected causal relationship to the study device(s) will be recorded in the subjects' case histories (source data, case report form). For all adverse events, sufficient information will be pursued and/or obtained so as to permit 1) an adequate determination of the outcome of the event (i.e., whether the event should be classified as a serious adverse event) and; 2) an assessment of the causal relationship between the adverse event and the study device.

Tufts Medical Center

Adverse events or abnormal test findings thought to be associated with the study device (ITN) will be followed until the event (or its sequel) or the abnormal test finding resolves or stabilizes at a level acceptable to the Investigator.

An abnormal test finding will be classified as an adverse event if one or more of the following criteria are met:

- The test finding is accompanied by clinical symptoms
- The test finding necessitates additional diagnostic evaluation(s) or medical/surgical intervention; including significant additional concomitant drug treatment or other therapy
- The test finding is considered an adverse event by the Investigator. Note: simply repeating a test finding, in the absence of any of the other listed criteria, does not constitute an adverse event.

The Investigator will promptly review documented adverse events and abnormal test findings to determine 1) if the abnormal test finding should be classified as an adverse event; 2) if there is a reasonable possibility that the adverse event was caused by the study device; and 3) if the adverse event meets the criteria for a serious adverse event.

If the Investigator's final determination of causality is "unknown and of questionable relationship to the study device", the adverse event will be classified as associated with the use of the study device for reporting purposes. If the Investigator's final determination of causality is "unknown but not related to the study device", this determination and the rationale for the determination will be documented in the respective subject's case history (source data or case report form).

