10.6 Safety Analysis

The primary safety variable monitored will be the occurrence of adverse events. The severity of each adverse event observed will be evaluated as serious or not serious as defined by the Tufts

Tufts Medical Center

HSC and the occurrence will be evaluated as expected or unexpected. The relationship of the event to the study medication will be assessed by the investigator as possibly, probably, or definitely related. Safety variables will be evaluated at screening and at all study visits. If adverse events occur, the first concern will be the safety of the study participants. Any serious adverse event occurring during the study period will be immediately reported to Tufts IRB. Directed questioning will be done to assess tolerability. Additional steps taken to assess safety will be followed as outlined in section 8.1 of this SUPP M form.

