11. DATA AND SAFETY MONITORING

11.1 Data and Safety Monitoring Plan

The PI, research fellows, research coordinators, and technicians involved with this protocol will be required to read the protocol, participate in a group meeting to discuss roles before the protocol is approved, and participate in weekly clinical research meetings. The pharmacy and the clinical fellows on the protocol will be required to read the protocol and separate meetings will be created to discuss roles as they relate to the protocol.

A copy of the approved protocol and study related materials will be placed on a shared network drive accessible to authorized research staff involved in this study and on IRBnet.org.

The primary safety variable monitored will be the occurrence of adverse events. The severity of each adverse event observed will be evaluated as outlined in section 10.6 by the treating investigator. The PI will be made aware of all AEs within one week. The ocular surface exam and IVCM imaging will only be performed by a research technician, fellow, or investigator to ensure adherence to the required tests and accurate assessments.

The study coordinator will be responsible for monitoring each visit to ensure that the procedures are performed as outlined in the protocol and documented appropriately.

Raw data collected for this study will be entered into a master database by the study coordinator, research technician, or fellow and uploaded for access to the principal investigator and all authorized research staff members on the U-Drive of password-protected computers located in the Cornea Research Department.

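### Adverse-event severity is recorded on a seriousness scale, so non-serious events, including nasal ones, get no intensity grade

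*Combined protocol and SAP*

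**What the plan says.** Section 8.1 (Safety Assessments) sets the rule: "The severity of each adverse event observed will be evaluated as serious or not serious". Section 10.6 (Safety Analysis) gives it again with a pointer to an institutional definition: "The severity of each adverse event observed will be evaluated as serious or not serious as defined by the Tufts" HSC. Section 11.1 (Data and Safety Monitoring Plan) adds no scale of its own: "The severity of each adverse event observed will be evaluated as outlined in section 10.6 by the treating investigator".

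Section 9.1 (Recording Requirements) lists two criteria for a serious event: "Is fatal (i.e., the adverse event actually causes or leads to death") and "Is life threatening (i.e., the adverse event, in the view of the investigator, places the patient at immediate risk of death"). It asks for enough information on each event to permit two things. One is a causality assessment. The other is "an adequate determination of the outcome of the event (i.e., whether the event should be classified as a serious adverse event").

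The same section makes severity one element of expectedness. Its definition of an unanticipated problem begins "unexpected (in terms of nature, severity, or frequency"), and its definition of an unanticipated adverse device effect also refers to severity.

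Appendix VI, the tolerability form, asks "how intensely have you experienced the following symptoms" and offers a five-step answer from None to Severe for three symptoms in each eye. A yes/no item about any other symptoms follows, with a free-text line. Section 7.4 (Follow-up Procedures) describes the form as covering discomfort in each eye.

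**The concern.** Seriousness is a regulatory threshold based on outcome. Severity is the intensity of the event. An event can be severe and not serious, and most harms that decide whether people keep using a device are of that kind. A plan that grades severity by seriousness has no place to record this.

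It matters here because safety and tolerability are listed secondary outcomes (section 10.2) and the safety of 90 days of daily use is part of the second specific aim (section 2.0). The device tip sits in the nose, and the exclusion criteria in section 4.2 show that the protocol recognises nasal risk, since they cover epistaxis, nasal surgery or trauma, and airway obstruction. At the minimum use stated in section 5.3, a patient who completes the study makes at least 2 × 90 = 180 applications. Mild and marked nasal events would be reported alike as non-serious. An event that is unexpected only because of its severity also has no recorded grade on which to base that judgement.

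**Working it through.** The plan states no figure on this point, and no sample size or event rate bears on it. The check is whether any part of the document gives an adverse event an intensity grade.

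1. **Rule for assessment (8.1).** Two levels, serious and not serious, under the name of severity.
2. **Rule for analysis (10.6).** The same two levels. No tabulation by intensity is planned.
3. **Rule for monitoring (11.1).** Refers to 10.6, so the same two levels.
4. **Information sought on each event (9.1).** Seriousness and causality. The outcome of the event is itself explained as its classification as serious or not, so this adds no third attribute.
5. **Where the threshold lies.** On the 9.1 list, only fatal and life-threatening events are serious. A nosebleed or nasal pain short of that is not serious, whatever its intensity. Section 10.6 points to another definition, which the document does not reproduce. A broader definition would move some events across the line, but it would still leave every event below the line ungraded.
6. **Where severity is needed.** Section 9.1 uses severity, beside nature and frequency or incidence, to decide whether an event is unexpected. Steps 1 to 4 supply no such grade.
7. **Other graded instruments.**
   - Appendix VI: 3 symptoms (itching, burning, foreign body sensation) × 2 eyes = 6 ratings, each on 5 levels. Nasal items: 0. A nasal symptom can enter only through the yes/no item and its free text, without a grade.
   - OPAS (Appendix III): a level for the worst non-eye pain, described as temples, back of head and cheek, and a percentage of time spent thinking about it. The nose is not named and bleeding is not covered.
   - Safety examination (8.1): the structures listed are all ocular.

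The result is 2 recorded levels, both of seriousness, 0 levels of intensity for adverse events, and 0 graded nasal items.

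**The case against.** The best case for the plan is that much of the safety information survives. The primary safety variable is the occurrence of adverse events, not of serious ones. Section 9.1 requires all events to be recorded, and they are classified by relatedness and expectedness. This stands, and it limits the point.

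It also rules out several stronger readings that a reader might infer:

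- *That the safety report could say only that no serious events occurred.* The documents do not support this. A large number of non-serious events would show in the counts.
- *That the trial grades no harm at all, or that Appendix VI is the sole graded instrument.* Neither is right. Appendix VI grades three eye symptoms, and OPAS grades face and head pain, so headache has a graded measure at visits. OPAS is an outcome measure, however, and not a grade attached to an adverse event.
- *That an event that ends device use could not be told from a trivial one.* This is too strong. The base unit logs use, level and duration (5.1), the diary records use (Appendix VII), and patients are asked about usage at the second and third visits (7.4). Stopping would be visible, although no section says that these data will be linked to adverse events.
- *That an upper confidence limit for zero serious events measures the problem.* Such a limit depends only on the number of patients and would be the same after the fix.

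It can also be said that the CRF and the institutional adverse-event policy are not reproduced, so a severity field may exist there. That is possible. Even so, the protocol states a two-level rule in two sections and plans no analysis by grade. Finally, this is a single-arm pilot of a device described as FDA-approved, so an elaborate safety analysis would be out of proportion. The change needed is small enough to meet that objection.

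**Conclusion.** The point holds in a limited form. Sections 8.1 and 10.6, and 11.1 by reference, use seriousness as the severity scale, so as written no non-serious event receives an intensity grade. Nasal events are the most exposed, because neither Appendix VI nor OPAS grades them. The loss is the ranking by intensity within the non-serious class, plus a grade on which to base the severity part of expectedness. Counts, relatedness and expectedness remain, and the primary endpoint is not affected. Sections 9.1 and 10.6 also rest on two sources for the meaning of serious, and these must be reconciled.

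This should be changed, since a stated aim and two secondary outcomes depend on it. The conclusion assumes that the unseen CRF and institutional policy add no severity grade. The statement that almost all device events would be non-serious further assumes that the 9.1 list is the one applied. The absence of a grade does not depend on that second assumption.

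**What to change.** - In sections 8.1 and 10.6, replace the current rule with two separate fields for each event: severity (mild, moderate, severe, each with a one-line definition) and seriousness (yes, no). Section 11.1 then follows by reference.
- In section 10.6, state that the number and proportion of patients with adverse events will be tabulated by severity and by relationship to the device.
- In Appendix VI, add nasal items such as nosebleed and nasal pain on the form's existing None-to-Severe scale. Amend the description of the form in section 7.4 (Follow-up Procedures) to match.
- Reconcile the list of serious criteria in section 9.1 with the institutional definition cited in section 10.6, and reproduce in the protocol whichever definition applies.

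The cost is one CRF field, a few questionnaire lines and one table. No extra visits are needed.
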